3.1. Study Rationale

Lilly is developing LY3202626, a synthetic small molecule which is an inhibitor of β -site amyloid precursor protein (APP)-cleaving enzyme [BACE]1, for the treatment of mild Alzheimer's disease (AD) dementia. This small molecule, at the 12 mg dose, has a high level of BACE1 inhibition (resulting in 90% reduction in A β), which may be a differentiating characteristic for efficacy if the effects at an enzymatic level translate clinically. It is hypothesized that inhibition of BACE1 may slow the progression of AD.

Study I7X-MC-LLCF (LLCF), a Phase 2 study, will assess if inhibiting the production of Aβ in the brain through BACE1 inhibition with LY3202626 can slow the progression of disease as assessed by biomarkers of neurodegeneration over 52 weeks of treatment. The ¹⁸F-AV-1451 positron emission tomography (PET) scan will be the primary outcome measure as a marker of disease progression for this study, to assess cerebral tau neurofibrillary tangle load and whether there are any changes with Aβ targeted BACE inhibitor treatment. The study will assess LY3202626 pharmacokinetics (PK) and pharmacodynamics (PD; plasma Aβ), biomarkers of amyloid pathology (florbetapir F 18 PET) and neurodegeneration (volumetric magnetic resonance imaging [vMRI] and cerebral perfusion). In addition, LY3202626, Aβ, and tau in cerebrospinal fluid (CSF) will be collected in a substudy to assess the PKs of LY3202626, PD (CSF Aβ), and neurodegeneration (CSF tau) within the central nervous system (CNS). Clinical outcomes including cognition, functional consequences of cognition, and safety will also be evaluated.

3.2. Background

Alzheimer's disease is a gradually progressive degenerative disease affecting older people that results in the slow decline of cognitive and behavioral functions with a characteristic early symptom of memory loss in patients (Takizawa et al. 2015). Currently available therapies for treatment of AD are able to variably reduce the symptoms without affecting the underlying pathology of the disease, so patients continue to decline clinically. Recent Phase 3 study failures in moderate AD (EPOCH study (press release [WWW]); Doody et al, 2014) suggest that treatment options may be limited once the disease has advanced. Thus, there is a significant need to develop a disease-modifying treatment that will slow the progression of this debilitating brain disorder, and a growing emphasis to move therapeutic trials for disease-modifying agents earlier in the disease.

After autopsy, patients with AD routinely display severe brain atrophy with neurofibrillary tangles and amyloid plaques (Cummings 2004). Although the definitive cause of the disease is not yet clearly understood, much evidence supports the hypothesis that amyloid β (A β) peptide aggregates to form amyloid plaques and acts as an initial trigger of the disease (Shankar et al. 2008). These plaques may be toxic to neurons and are believed to lead to synapse loss, neurofibrillary tangle formation, and neuronal cell death. Hence, inhibition of A β formation is a logical strategy towards developing a therapy for AD.

Amyloid β is part of the amyloid precursor protein (APP), which is a transmembrane protein widely expressed on the cell surface, particularly in neurons. The APP has been found to be cleaved through 2 cleavage pathways involving 3 secretase enzymes: α -secretase, γ -secretase, and β -secretase (now called β -site APP-cleaving enzyme [BACE]1). Cleavage of APP by α -secretase precludes the formation of A β as the site is located within the A β sequence. In the second pathway, β -secretase cleaves the APP molecule, generating membrane-associated C99 and releasing a larger secreted fragment called secreted APP (sAPP) β . γ -Secretase then cleaves C99 in a heterogeneous fashion within the membrane releasing a variety of A β species that aggregate in protofibrils, then fibrils, which seem to comprise the mass of A β plaques in AD brain tissue (Turner et al. 2003). While both γ - and β -secretase inhibition represent effective means of precluding the formation of A β , β -secretase inhibition may provide improved safety and tolerability (Doody et al. 2013).

LY3202626, a synthetic small molecule, potent BACE1 inhibitor is being developed for the treatment of AD dementia. LY3202626 has been shown to reduce plasma and CSF $A\beta_{1.40}$ and $A\beta_{1.42}$ in mice, dogs, and humans. The Phase 1 clinical Study I7X-EW-LLCA (LLCA) investigated the safety, tolerability, PK, and PD of single- and multiple-ascending doses of LY3202626 given orally, in healthy subjects and patients with AD. In this study, single doses of LY3202626 from 0.1 mg to 45 mg were well tolerated, and demonstrated a robust, prolonged reduction in plasma $A\beta$ concentrations. LY3202626 was also administered as single daily doses of 1 mg to 26 mg for 14 days. In this multiple dose portion of the trial, LY3202626 was well tolerated, and a dose-dependent reduction in both plasma and CSF $A\beta$ concentrations was observed. At steady-state, 1 mg LY3202626 was associated with an approximate 50% reduction in CSF $A\beta_{1.40}$, while at 6 mg, reductions of approximately 75% were observed. At 26 mg, CSF $A\beta_{1.40}$ reductions exceeded 90%. These projected CSF $A\beta_{1.40}$ reductions will be verified in a mild AD dementia population in the lumbar puncture (LP) addendum to this study.

This Phase 2 study will assess if inhibiting the production of AB in the brain at doses projected to reduce CSF Aβ by 70% and 90%, can slow the progression of disease as assessed by biomarkers of neurodegeneration over 52 weeks of treatment. Data from the 12 mg dose arm will be used to assess the effect of greatest BACE inhibition on tau PET changes, other biomarkers of disease progression, and clinical outcomes. All outcomes will also be assessed for the 3 mg dose arm though the primary focus will be safety and tolerability of the 3 mg dose over 52 weeks of exposure in the mild AD population. Tau is a protein that accumulates in the brains of AD patients and is a defining pathology of the disease. The density and neuroanatomical localization of tau neurofibrillary tangles correlate strongly with neurologic symptoms and AD progression. Until recently, the only way to determine tau pathological changes in the brain was at autopsy. The recent development of the ¹⁸F-AV-1451 PET tracer, has allowed for the first time, the ability to detect and measure tau protein in the brain of patients suspected of suffering from AD (Xia et al. 2013). Early use of this tracer shows increasing signal from healthy controls to mild cognitive impairment due to AD to mild to moderate AD. The anatomical distribution corresponds well to the pathological staging of Braak and Braak (Chien et al. 2013). The signal also increases with progression of disease, both in intensity and in spread to other cortical regions. The ¹⁸F-AV-1451 PET scan will be the primary outcome measure as a marker of

neuropathological disease progression for this study, to assess for cerebral tau neurofibrillary tangle load and whether there are any changes with $A\beta$ targeted BACE inhibitor treatment.

The biomarker florbetapir F 18 is a PET ligand that binds to fibrillar amyloid plaque. This biomarker can provide a qualitative and quantitative measurement of brain plaque load in patients with mild AD dementia. The absence of significant florbetapir F 18 signal indicates that those patients clinically manifesting dementia lack evidence of amyloid pathology. As such, implementation of florbetapir F 18 will provide a screening tool for entry into the clinical trials and provide a confirmation of amyloid pathology. Florbetapir F 18 PET also provides quantitative assessment of amyloid in the brain and can assess whether Aβ lowering by BACE inhibition can reduce amyloid deposition.

Alzheimer's disease progression is also associated with cerebral atrophy and hypoperfusion, which will be assessed by vMRI and the early post-injection data from the florbetapir F 18 PET scans, respectively.

3.3. Benefit/Risk Assessment

More information about the known and expected benefits, risks, serious adverse events (SAEs) and reasonably anticipated adverse events (AEs) of LY3202626 are to be found in the Investigator's Brochure (IB).

4. Objectives and Endpoints

Table LLCF.1 shows the objectives and endpoints of the study.

Table LLCF.1. Objectives and Endpoints

Objectives	Endpoints					
Primary To assess the change from baseline in ¹⁸ F-AV-1451 PET after treatment with LY3202626 3 mg or 12 mg per day compared with placebo for 52 weeks among patients with mild AD dementia and evidence of brain amyloid.	The change in SUVr of ¹⁸ F-AV-1451 PET from baseline to 52 weeks. The change will be compared between the LY3202626 doses (3mg and 12mg) and placebo.					
• To evaluate the safety and tolerability of LY3202626 (3 mg and 12 mg per day) compared with placebo	Standard safety assessments:					
 To assess peripheral PK and PD of LY3202626 (3 mg and 12 mg per day) over 52 weeks To assess change from baseline in cognition after 52 weeks of treatment among patients treated with LY3202626 (3 mg and 12 mg per day) compared with placebo. To assess change from baseline in function 	 Plasma Pharmacokinetics of LY3202626 Plasma Pharmacodynamics Aβ₁₋₄₀, Aβ₁₋₄₂, Aβ_{1-x} ADAS-Cog₁₃ 					
 To assess change from baseline in function after 52 weeks among patients treated with LY3202626 (3 mg and 12 mg per day) compared with placebo To assess change from baseline in a composite measure of cognition and function after 52 weeks among patients treated with LY3202626 (3 mg and 12 mg per day) compared with placebo 	ADCS-iADLiADRS					

Objectives and Endpoints

Objectives	Endpoints
Exploratory	
 To assess change in cognition after 52 weeks among patients treated with LY3202626 (3 mg and 12 mg per day) compared with placebo 	• MoCA
 To assess change in function after 52 weeks among patients treated with LY3202626 (3 mg and 12 mg per day) compared with placebo 	• FAQ
 To assess change in cognition after 52 weeks among patients treated with LY3202626 (3 mg and 12 mg per day) compared with placebo 	• MMSE
 To assess change in everyday functioning after 52 weeks among patients treated with LY3202626 (3 mg and 12 mg per day) compared with placebo 	• ECog
 To assess change in neuropsychiatric symptoms after 52 weeks among patients treated with LY3202626 (3 mg and 12 mg per day) compared with placebo 	• NPI
 To assess change in subjective quality of life after 52 weeks among patients treated with LY3202626 (3 mg and 12 mg per day) compared with placebo 	• BASQID
 To assess change from baseline in rCBF after 52 weeks among patients treated with LY3202626 (3 mg and 12 mg per day) compared with placebo. 	SUVr cerebral perfusion from early post- injection florbetapir PET scan
 To assess change from baseline in brain amyloid after 52 weeks among patients treated with LY3202626 (3 mg and 12 mg per day) compared with placebo 	Florbetapir F 18 PET SUVr
 To assess change from baseline in brain and brain regional volumes after 52 weeks among patients treated with LY3202626 (3 mg and 12 mg per day) compared with placebo. 	Volumetric MRI

[figure not shown]
Abbreviations: AD = Alzheimer's disease; ADAS-Cog₁₃ = Alzheimer's Disease Assessment Scale - Cognitive subscale, 13-item version; ADCS-iADL = Alzheimer's Disease Cooperative Study-Activities of Daily Living inventory, instrumental items; AE = adverse event; ARIA = amyloid-related imaging abnormality; BASQID = Bath Assessment of Subjective Quality of Life in Dementia; C-SSRS = Columbia Suicide Severity Rating Scale; ECG = electrocardiogram; ECog = Everyday Cognition; FAQ = Functional Activities Questionnaire; iADRS = integrated Alzheimer's Disease Rating Scale; MMSE = Mini-Mental Status Examination; MoCA = Montreal Cognitive Assessment; MRI = magnetic resonance imaging; NPI = Neuropsychiatric Inventory; PET = positron emission tomography; PD = pharmacodynamic; PK = pharmacokinetic; rCBF = regional cerebral blood flow; SUVr= summary uptake value ratio.

5. Study Design

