### 3. Revision History

Statistical Analysis Plan (SAP) Version 1 was approved prior to unblinding.

Statistical Analysis Plan (SAP) Version 2 was approved prior to final database lock. Due to early termination of the study, certain analyses were removed or simplified, while others were clarified. The changes in SAP version 2 are summarized below:

- Clarified that change from baseline to last observation is to be used in ANCOVA analysis if Week 52 observation is not available (Section [5.1](#))
- Removed the exploratory analysis on subjects with study partner change during the study (previously Section 5.11 in Version 1)
- Clarified the analysis for changes from baseline in NPI total score and BASQID total score will be ANCOVA instead of MMRM because they were collected only once during post-baseline visits (Section [5.11.2](#))
- Specified the cut-off for defining Tau subgroups and removed the subgroup analysis regarding race and country (Section [5.11.3](#))
- Removed sensitivity analysis on Tau PET using percentage changes from baseline (previously Section 5.12.4 in Version 1)
- Simplified analysis of CSF biomarkers to listing of values by visit by treatment due to very limited number of subjects participated in the CSF addendum (Section [5.12.2](#))
- Added analysis on annualized change in imaging biomarkers (vMRI, AV-45 PET, AV-1451 PET) because majority of the subjects would not have Week 52 observation due to early termination of the study (Section [5.12.5](#))
- Added an incidence summary for treatment-emergent CSSRS findings (Section [5.13.8.1](#))
- Simplified and clarified the analysis for categorical eye exam and eye imaging data (Section [5.13.8.3](#))

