## 5. A Priori Statistical Methods

### 5.1. General Considerations

All tests of treatment effects of biological efficacy or clinical efficacy will be conducted at a 1-sided  $\alpha=.10$ , unless otherwise stated. Safety assessments will be conducted at a 2-sided  $\alpha=.05$ .

A repeated measures analysis refers to a restricted maximum likelihood (REML)-based, mixed effects repeated measures analysis using all the longitudinal observations at each post-baseline visit.

All analyses will follow the intent-to-treat (ITT) principle unless otherwise specified. An ITT analysis is an analysis of data by the groups to which subjects are assigned by random allocation, even if the subject does not take the assigned treatment, does not receive the correct treatment, or otherwise does not follow the protocol.

When change from baseline is assessed, subjects will be included in the analysis only if both a baseline and a postbaseline measure are available. Unless otherwise defined, Visit 3 is the baseline visit, and baseline value is defined as last value available before or at Visit 3.

All total and subscale scores will be derived from individual items. If any individual item is missing, the corresponding total and subscale scores will be considered missing, except for the ADAS-Cog13 and ADCS-iADL, which will be imputed.

A repeated measures analysis model will include the fixed, categorical effects of treatment, visit, and treatment-by-visit interaction, as well as the continuous, fixed covariates of baseline, baseline-by-visit interaction, and age at baseline.

When an analysis of covariance (ANCOVA) model is used to analyze a continuous efficacy variable, the model will contain the main effects of treatment with baseline value and age at baseline added as covariates. For ANCOVA analysis on change from baseline to Week 52 endpoint, change from baseline to last observation during treatment period will be used if patients do not have Week 52 observation available.

Categorical comparisons between treatment groups will be performed using Fisher's exact tests or logistic regression where appropriate.

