### 5.12.4. Analyses of perfusion PET Data

An additional perfusion-weighted image will be acquired at each florbetapir PET scanning visit, with no additional tracer injection, by utilizing the initial wash-in of florbetapir to the brain. These images will provide a perfusion (or blood flow) map of the brain at each time point. In AD, cerebral perfusion is reduced, especially in temporal and parietal areas, and this pattern of hypoperfusion closely mirrors the hypometabolism pattern observed using 18F-fluorodeoxyglucose (FDG)-PET. As such, the perfusion PET images provide a biomarker of resting brain function. Changes in florbetapir perfusion PET between the baseline and follow-up scans will be compared across treatment groups and to total exposure to LY3202626.

The analysis of change from baseline to the post-baseline visit of the composite summary SUVr of perfusion scan will be performed using an ANCOVA model with baseline biomarker result and baseline age as covariates and treatment as categorical effect.

The analyses of change from baseline will also be conducted for SUVr of each individual Region of Interest (ROI).

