### **5.12.5. Analyses of Volumetric MRI Data**

Brain atrophy is one of the signature biological changes associated with AD, with shrinkage of the medial temporal lobe (including the hippocampus) and ventricular enlargement particularly prominent. The volume of different brain structures and measures of atrophy can be accurately quantified from vMRI scans. Magnetic resonance imaging changes in brain volume from baseline to after 52 weeks of treatment (or early discontinuation) will be quantified. Measurements of brain structural changes, including, but not limited to, whole brain, ventricles and hippocampus will be evaluated. Brain structural changes will be compared across treatment groups and to total exposure to LY3202626.

Analyses of the following vMRI parameters will be conducted:

- Right hippocampal volume ( $\text{mm}^3$ )
- Left hippocampal volume ( $\text{mm}^3$ )
- Right hippocampal volume ( $\text{mm}^3$ ) + Left hippocampal volume ( $\text{mm}^3$ )
- Right entorhinal cortex ( $\text{mm}^3$ )
- Left entorhinal cortex ( $\text{mm}^3$ )
- Atrophy of Total whole brain volume ( $\text{cm}^3$ )
- Enlargement of Ventricular volume ( $\text{cm}^3$ )

To evaluate the changes in vMRI data after treatment, an ANCOVA model will be used to compare change from baseline to 52 weeks. The change from baseline to the endpoint visit will be the dependent variable. The model for the fixed effects will include terms for the following independent effects: baseline vMRI value, age at baseline, and treatment.

In addition, annualized change in imaging biomarkers (vMRI, AV-45 and AV-1451) for each patient will be calculated using the change at the last post-baseline visit. The annualized change will be compared among the treatment groups with the same ANCOVA model described above.

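### The annualized-change analysis added in SAP version 2 leaves out perfusion PET, so the rCBF comparison between arms takes no account of unequal scan intervals (minor; mainly affects 3 mg versus placebo)

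*Protocol*

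**What the plan says.** Protocol Section 4 (Table LLCF.1) and SAP Section 4.3 set an exploratory objective on regional cerebral blood flow: "To assess change from baseline in rCBF after 52 weeks among patients treated with LY3202626". The endpoint is perfusion SUVr. Under the Schedule of Activities and Protocol Sections 7.1.3 and 9.1.4, it is acquired in the florbetapir session, at screening and again at Week 52 or early discontinuation. Imaging at early discontinuation is done only if at least 24 weeks have passed since the baseline measurement.

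The SAP revision history (Section 3) records the response to early termination: "Added analysis on annualized change in imaging biomarkers (vMRI, AV-45 PET, AV-1451 PET) because majority of the subjects would not have Week 52 observation". The operative sentence in SAP Section 5.12.5 reads "annualized change in imaging biomarkers (vMRI, AV-45 and AV-1451) for each patient will be calculated using the change at the last post-baseline visit". Neither names perfusion.

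Perfusion has its own section, SAP 5.12.4: "The analysis of change from baseline to the post-baseline visit of the composite summary SUVr of perfusion scan will be performed using an ANCOVA model". The only adjustments named there are for the patient's starting perfusion value and age. That section also says that perfusion changes "will be compared across treatment groups and to total exposure to LY3202626", without giving a model. SAP Section 5.1 adds a general rule for ANCOVA analyses of the Week 52 endpoint, under which "change from baseline to last observation during treatment period will be used if patients do not have Week 52 observation available".

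**The concern.** The reason given for annualizing applies to perfusion exactly as it does to amyloid PET. Both images come from one tracer injection at one visit, so each patient has the same interval for both. The SAP annualizes one and not the other, and gives no reason.

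The perfusion model has no term for the time between scans. Protocol Section 3.2 associates hypoperfusion with disease progression, so a longer interval should show more decline whatever the treatment. If intervals differ between arms, part of any difference is timing. Randomization was 1:1:1 only until about 45 patients per arm, and afterwards 12 mg or placebo only. At a calendar stop, 3 mg patients have therefore tended to be in the study longer than the pooled placebo patients. For vMRI, AV-45 and AV-1451 the annualized result offers a check on this. For perfusion there is none, and the imaging results are not on a common footing.

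**Working it through.** The plan states no figure to reproduce here. It gives no slope, standard deviation, accrual dates or stop date for perfusion. The check is therefore a comparison of texts, followed by an illustration on stated assumptions.

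**1. Does AV-45 include perfusion?** SAP 5.12.3 describes AV-45 as amyloid imaging and refers to Appendix 4 for the complete list of AV-45 parameters. That list has no perfusion measure, and perfusion is handled separately in 5.12.4. The natural reading is that it is not included.

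**2. What does the interval do to a raw change?** Assume linear change. A scan taken T weeks after baseline carries T/52 of the one-year change: 24/52 = 46%, 36/52 = 69%, 48/52 = 92%. A difference of d weeks in mean interval between arms creates a difference of d/52 of the one-year change with no drug effect: 4/52 = 8%, 8/52 = 15%, 12/52 = 23%.

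**3. How large might the gap be?** Inputs from the documents: about 380 patients; 1:1:1 for the first 3 × 45 = 135, then 1:1; florbetapir baseline at Week -6; the 24-week rule; under half of patients at Week 52. Assumptions: uniform accrual, a single calendar stop and no other dropout. The interval is min(52, stop − entry) + 6 weeks, counted if it is at least 24.

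One case in full, with 380 patients over 80 weeks (4.75 per week) and a stop at week 87:
- The 1:1:1 stage ends at 135/4.75 = week 28.4. Week 52 is reached by those who entered by 87 − 52 = week 35, which is 35/80 = 44% of patients.
- 3 mg: all 45 reach Week 52, so the mean interval is 58 weeks.
- Placebo at 58 weeks: 45 + (35 − 28.4) × 4.75/2 ≈ 60.6 patients.
- Placebo entering between weeks 35 and 69: 34 × 4.75/2 = 80.75 patients, with intervals falling from 58 to 24 weeks, mean 41. Later entrants have no qualifying scan.
- Placebo mean: (60.6 × 58 + 80.75 × 41)/141.4 ≈ 48.3 weeks.
- Ratio 58/48.3 = 1.20; gap 9.7 weeks, or 9.7/52 = 19% of the one-year change.

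The same calculation over 315 to 380 patients, accrual over 60 to 104 weeks and a stop at weeks 70 to 104 gives:

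| Scenarios | 3 mg / placebo interval ratio |
|---|---|
| All | about 1.01 to 1.28 |
| Under half of patients at Week 52, as the SAP states | about 1.10 to 1.28 |

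An earlier stop with slow accrual removes the gap. With 315 patients over 104 weeks, the 1:1:1 stage lasts 135/(315/104) = 44.6 weeks. With a stop at week 60, only entrants up to week 60 + 6 − 24 = 42 have a qualifying scan. All of them come from the 1:1:1 stage, and the ratio is 1.00.

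**4. 12 mg versus placebo.** These arms share the same allocation ratio in both stages, so their expected intervals are equal apart from differential dropout.

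**The case against.** The strongest reply is that little depends on this. The endpoint is exploratory. Protocol Section 10.3.3.3 makes 12 mg versus placebo the primary comparison for such endpoints, and Protocol Section 3.2 puts the main focus of the 3 mg arm on safety and tolerability. The annualized analysis is supplementary for the other biomarkers too. All of this stands and limits the severity.

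It can also be said that AV-45 is the tracer's name (Protocol Appendix 1 equates it with florbetapir), so the list could be read to include the early-phase image. Appendix 4 of the SAP and the separate section for perfusion weigh against that reading, but the wording could be clearer.

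A reader might infer that the SAP labels every perfusion scan as a Week 52 value. Section 5.12.4 does not say so; it refers to the post-baseline visit. The label follows only if the Section 5.1 rule is combined with the 52-week objective. A reader might also infer that the ANCOVA is the only use of perfusion data. Section 5.12.4 plans a comparison with total exposure as well, although this is not a time-adjusted comparison between arms.

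Last, annualizing is not free. It assumes linear change, and at 24 weeks it multiplies the change by 52/24 = 2.17, and so multiplies the scan-noise variance by 2.17² ≈ 4.7. This is a reason to report it alongside the raw-change ANCOVA and not to substitute it.

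**Conclusion.** The omission is real and of minor severity. As written, the comparison of perfusion between arms rests on raw change to the post-baseline scan, adjusted for baseline value and age but not for scan interval. SAP version 2 recognized this problem for the other imaging measures.

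The bias of concern lies in 3 mg versus placebo. If perfusion declines over time, an inert 3 mg dose would tend to show more decline than placebo. The ratio of roughly 1.1 to 1.3 in mean interval depends on uniform accrual, a stop at week 70 or later and no other dropout, and turning it into a difference in perfusion requires linear change. It is an illustration and not an estimate for this trial. The documents do not support a narrower figure, or any statement on whether the difference would be detectable with about 45 patients.

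The documents also do not support extending the concern to 12 mg versus placebo, which is nearly balanced on interval, or to any primary or secondary conclusion.

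**What to change.** In SAP Section 5.12.5, and in the matching line of Section 3, add perfusion PET (composite SUVr) to the measures analysed as annualized change, and state that the interval is computed from actual scan dates. Add a cross-reference in Section 5.12.4. Report the annualized result beside the 5.12.4 ANCOVA, not in its place, and tabulate scan interval by arm so that the reader can see whether 3 mg and placebo differ. If perfusion was left out on purpose, give the reason instead.

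The cost is a phrase in the SAP, one more run of a model already planned, and one table from dates that should already be on file. The price in interpretation is the linearity assumption and the extra noise from short intervals, and both should be stated with the result.
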